8.4.3.2. Columbia Suicide Severity Rating Scale (C-SSRS)

The C-SSRS is a clinician-rated instrument that captures the occurrence, severity, and frequency of suicide-related ideations and behaviours during the assessment period. Suicidal ideation is classified on a 5-item scale: 1 (wish to be dead), 2 (nonspecific active suicidal thoughts), 3 (active suicidal ideation with any methods [not plan] without intent to act), 4 (active suicidal ideation with some intent to act, without specific plan), and 5 (active suicidal ideation with specific plan and intent). The C-SSRS also captures information about the intensity of ideation, specifically the frequency, duration, controllability, deterrents, and reasons for the most severe types of ideation. Suicidal behavior is classified on a 5-item scale: 0 (no suicidal behavior), 1 (preparatory acts or behavior), 2 (aborted attempt), 3 (interrupted attempt), and 4 (actual attempt). More than 1 classification can be selected provided they represent separate episodes. For actual attempts only, the actual or potential lethality is classified for the initial, most lethal, and most recent attempts. C-SSRS will be evaluated at Day 1, Week 24, Week 48, Week 72 and Week 96.

The severe level of suicidal ideation 5 items from low to high:

- 1: Wish to be dead
- 2: Non-specific active suicidal thoughts
- 3: Active suicidal ideation with any methods (not plan) without intent to act
- 4: Active suicidal ideation with some intent to act, without specific plan
- 5: Active suicidal ideation with specific plan and intent

The severe level of suicidal behavior 5 items from low to high:

- 1: Preparatory Acts or Behavior
- 2: Aborted Attempt
- 3: Interrupted Attempt
- 4: Actual Attempt
- 5: Suicidal Behavior

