### **12.7 Columbia-Suicide Severity Rating Scale (C-SSRS)**

The clinician will attend a certified rater training for the C-SSRS, to ensure consistent and accurate ratings.

The C-SSRS is a clinician-rated instrument that captures the occurrence, severity, and frequency of suicide-related ideations and behaviors during the assessment period. The C-SSRS must be administered by appropriately trained site personnel. Suicidal ideation is classified on a 5-item scale: 1 (wish to be dead), 2 (nonspecific active suicidal thoughts), 3 (active suicidal ideation with any methods [not plan] without intent to act), 4 (active suicidal ideation with some intent to act, without specific plan), and 5 (active suicidal ideation with specific plan and intent). The C-SSRS also captures information about the intensity of ideation, specifically the frequency, duration, controllability, deterrents, and reasons for the most severe types of ideation. Suicidal behavior is classified on a 5-item scale: 0 (no suicidal behavior), 1 (preparatory acts or behavior), 2 (aborted attempt), 3 (interrupted attempt), and 4 (actual attempt). More than 1 classification can be selected provided they represent separate episodes. For actual attempts only, the actual or potential lethality is classified for the initial, most lethal, and most recent attempts. C-SSRS assessments are presented in Appendix 3.

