**Appendix 3      Columbia-Suicide Severity Rating Scale (C-SSRS) Example**

**COLUMBIA-SUICIDE SEVERITY  
RATING SCALE  
(C-SSRS)**

Since Last Visit

Version 1/14/09

*Posner, K.; Brent, D.; Lucas, C.; Gould, M.; Stanley, B.; Brown, G.; Fisher, P.; Zelazny, J.; Burke, A.; Oquendo, M.; Mann, J.*

*Disclaimer:*

*This scale is intended to be used by individuals who have received training in its administration. The questions contained in the Columbia-Suicide Severity Rating Scale are suggested probes. Ultimately, the determination of the presence of suicidal ideation or behavior depends on the judgment of the individual administering the scale.*

*Definitions of behavioral suicidal events in this scale are based on those used in The Columbia Suicide History Form, developed by [name] and [name], Conte Center for the Neuroscience of Mental Disorders (CCN/MD), New York State Psychiatric Institute, [name]. (Oquendo M. A., Halberstam B. & Mann J. J., Risk factors for suicidal behavior: utility and limitations of research instruments. In M.B. First [Ed.] Standardized Evaluation in Clinical Practice, pp. 103-130, 2003.)*

*For reprints of the C-SSRS contact [name]., New York State Psychiatric Institute, [name]; inquiries and training requirements contact [contact]*

*© 2008 The Research Foundation for Mental Hygiene, Inc.*

SUICIDAL IDEATION		Since Last Visit																																													

Ask questions 1 and 2. If both are negative, proceed to "Suicidal Behavior" section. If the answer to question 2 is "yes", ask questions 3, 4 and 5. If the answer to question 1 and/or 2 is "yes", complete "Intensity of Ideation" section below.
 
1. Wish to be Dead Subject endorses thoughts about a wish to be dead or not alive anymore, or wish to fall asleep and not wake up. Have you wished you were dead or wished you could go to sleep and not wake up?
 
If yes, describe:
																																															

2. Non-Specific Active Suicidal Thoughts General, non-specific thoughts of wanting to end one's life/commit suicide (e.g., "I've thought about killing myself") without thoughts of ways to kill oneself/associated methods, intent, or plan during the assessment period. Have you actually had any thoughts of killing yourself?
 
If yes, describe:
																																															

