Has subject engaged in Non-Suicidal Self-Injurious Behavior? Interrupted Attempt: When the person is interrupted (by an outside circumstance) from starting the potentially self-injurious act (if not for that, actual attempt would have occurred). Overdose: Person has pills in hand but is stopped from ingesting. Once they ingest any pills, this becomes an attempt rather than an interrupted attempt. Shooting: Person has gun pointed toward self, gun is taken away by someone else, or is somehow prevented from pulling trigger. Once they pull the trigger, even if the gun fails to fire, it is an attempt. Jumping: Person is poised to jump, is grabbed and taken down from ledge. Hanging: Person has noose around neck but has not yet started to hang - is stopped from doing so. Has there been a time when you started to do something to end your life but someone or something stopped you before you actually did anything? If yes, describe: _____		Yes  No   Total # of interrupted _____
Aborted Attempt: When person begins to take steps toward making a suicide attempt, but stops themselves before they actually have engaged in any self-destructive behavior. Examples are similar to interrupted attempts, except that the individual stops him/herself, instead of being stopped by something else. Has there been a time when you started to do something to try to end your life but you stopped yourself before you actually did anything? If yes, describe: _____		Yes  No   Total # of aborted _____
Preparatory Acts or Behavior: Acts or preparation towards imminently making a suicide attempt. This can include anything beyond a verbalization or thought, such as assembling a specific method (e.g., buying pills, purchasing a gun) or preparing for one's death by suicide (e.g., giving things away, writing a suicide note). Have you taken any steps towards making a suicide attempt or preparing to kill yourself (such as collecting pills, getting a gun, giving valuables away or writing a suicide note)? If yes, describe: _____		Yes  No   
Suicidal Behavior: Suicidal behavior was present during the assessment period?		Yes  No   
Suicide:		Yes  No   

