9.3.2. Columbia Suicide Severity Rating Scale (C-SSRS)

The C-SSRS will be analyzed and listed. The frequency and percentage of subjects with each response for suicidal ideation, intensity of ideation, and suicidal behavior items will be summarized for the treatment period (Weeks 24-since last visit, Week 48-since last visit, Week 72-since last visit and Week 96-since last visit) in MT-1186-A03. The distribution of responses for most severe suicidal ideation and suicidal behavior will also be presented for the treatment period.

1. The counting method of suicidal ideation:

In the treatment period, the subject who has at least one of each suicidal ideation 5 items will be counted once. In case subjects will report suicidal ideation several times within this period, then the subject will be counted in the most severe suicidal ideation item.

2. The counting method of suicidal behavior:

In the treatment period, the subject who has at least one of each suicidal behavior 5 items and non-suicidal self-injurious behavior item will be counted once. In case subjects will report suicidal behavior with non-suicidal self-injurious behavior several times within this period, then the subject will be counted in the most severe suicidal behavior item.

3. The counting method of suicidal ideation or suicidal behavior

In the treatment period, the subjects who meets the criteria of (1) or (2) will be counted.

4. The counting method of non-suicidal self-injurious behavior item

In the treatment period the subjects who has non-suicidal self-injurious behavior item will be counted.

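### The SAP's C-SSRS severity ranking puts a yes/no summary item above actual attempt; the orthostatic reference posture and the platelet conversion also need correcting

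*SAP*

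**What the plan says.** **C-SSRS.** SAP 8.4.3.2 describes suicidal behavior on a scale from 0 (none) to 4, whose upper end reads "3 (interrupted attempt), and 4 (actual attempt)". Protocol 12.7 gives the same scale: "Suicidal behavior is classified on a 5-item scale: 0 (no suicidal behavior)" and so on up to 4. SAP 8.4.3.2 then adds a list ordered from low to high, numbered 1 to 5, whose top entry is "5: Suicidal Behavior".

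Protocol Appendix 3, titled "Columbia-Suicide Severity Rating Scale (C-SSRS) Example", shows how the item is asked: "Suicidal behavior was present during the assessment period", answered yes or no. Completed suicide is the next item on the form, also yes or no, and has no place in the SAP list. Self-injury without suicidal intent is another separate question: "Has subject engaged in Non-Suicidal Self-Injurious Behavior".

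SAP 9.3.2 plans a distribution of most severe behavior over the treatment period. Under its counting rule 2, when there are several reports, "then the subject will be counted in the most severe suicidal behavior item". It also plans an item-level table: "The frequency and percentage of subjects with each response for suicidal ideation, intensity of ideation, and suicidal behavior items will be summarized". Rule 2 names self-injury alongside the five behavior items, rule 3 refers back to rule 2, and rule 4 counts self-injury on its own.

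**Orthostatic readings.** SAP 8.4.3.5 defines orthostatic hypotension by comparing standing with supine. SAP 9.3.4 tabulates that definition by visit and summarizes the supine-minus-standing difference. Protocol 12.3, and the six orthostatic change criteria in the same SAP 8.4.3.5, run from seated to standing at 1 and 3 minutes.

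**Platelets.** SAP 8.4.3.3 says that values in /mm³ are converted to 10⁹/L by multiplying by 1000. The limits for potentially clinically significant values (PCSV) are given in /mm³.

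**The concern.** The Suicidal Behavior item records whether any behavior occurred; it is not a more serious act than an actual attempt. A most-severe rule applied to a list with such an item at the top can move a subject with only a preparatory act into the highest category. C-SSRS is one of the primary safety endpoints in SAP 3.2.1, and the most-severe distribution is also called for in protocol 17.3.5.4. The protocol's scale does not override the list, because SAP section 2 says that the SAP's statistical details supersede the protocol's.

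The orthostatic wording raises a similar problem of derivation. Supine readings come from the routine procedure in protocol 12.2, which also accepts a position only as near to supine as the subject can manage. Read literally, the hypotension table sets a reading from one procedure against a standing reading from another, and does not say which of the two standing readings is meant. SAP section 11, on changes from the protocol, does not mention this.

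**Working it through.** **1. C-SSRS: the two lists side by side**

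| Level | Scale text (SAP 8.4.3.2, protocol 12.7) | Low-to-high list (SAP 8.4.3.2) |
|---|---|---|
| 0 | no behavior | not listed |
| 1 | preparatory acts | preparatory acts |
| 2 | aborted attempt | aborted attempt |
| 3 | interrupted attempt | interrupted attempt |
| 4 | actual attempt | actual attempt |
| 5 | none | Suicidal Behavior |

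Four specific yes/no items give 2⁴ = 16 patterns, of which 16 − 1 = 15 contain at least one behavior.

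- On the 0-4 scale, the number of patterns whose maximum is k is 2^(k−1). That gives 1, 2, 4 and 8 for k = 1 to 4, and 1 + 2 + 4 + 8 = 15.
- On the 1-5 list, let S = 1 if the summary item is yes. The assigned level is max(k, 5S). If S = 1 whenever any specific item is yes, this is 5 for all 15 patterns. The distribution over levels 1 to 5 is 0/0/0/0/15.
- If the summary item is not collected or not used as level 5, or if level 5 was meant as completed suicide and none occurred, the distribution is 1/2/4/8/0 and nothing collapses.

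These are counts of possible answer patterns, not of expected subjects. The documents do not give the number of subjects with any behavior.

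**2. Orthostatic reference**

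Supine − standing = (supine − seated) + (seated − standing). The two definitions therefore classify a subject differently whenever the supine-to-seated difference carries the drop across a threshold.

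An illustration with assumed systolic readings: supine 128, seated 120, standing 106 at 1 minute and 110 at 3 minutes.

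- From supine: 128 − 106 = 22 and 128 − 110 = 18.
- From seated: 120 − 106 = 14 and 120 − 110 = 10.

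One of the four pairings reaches the 20 mmHg limit. The readings were chosen to show that the choice can matter; they say nothing about how often it would. Subjects classified on symptoms alone do not change.

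**3. Platelet conversion**

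The SAP's stated factor is × 1000 from /mm³ to 10⁹/L. Since 1 L = 10⁶ mm³, x per mm³ = x × 10⁶ per L = x × 10⁶/10⁹ = x/1000 in units of 10⁹/L. The stated factor is not reproduced.

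- Correct: 100,000/mm³ ÷ 1000 = 100 × 10⁹/L, and 700,000/mm³ ÷ 1000 = 700 × 10⁹/L.
- As written: 100,000 × 1000 = 100,000,000, which is 100,000,000/100 = 10⁶ times too large.
- Opposite direction: 100 × 10⁹/L × 1000 = 100,000/mm³, which is correct and equals the SAP's low limit.

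**The case against.** The best case for leaving this alone is that the consequences are conditional and small.

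- **The C-SSRS collapse needs three things**: the summary item is collected, it is marked whenever a specific item is marked, and it is programmed as level 5. The Appendix 3 form is only an example and the eCRF is not available. This stands, and the collapse can be stated only as conditional.
- **Rule 2 sends a subject to the most severe item only after several reports**, so it does not clearly reach someone with a single report. This also stands for the rule itself. The planned most-severe distribution is a separate sentence without that restriction, so the ranking is still used.
- **Level 5 may be a slip for completed suicide**, the next item on the form. That is possible. Then only the label is wrong, but it still names the wrong item.
- **Little information would be lost.** The item-level frequencies and listings keep preparatory acts and attempts apart. The analyses are descriptive, and any suicidal behavior at Visit 1 is an exclusion (protocol 9.4), so few subjects may be involved. All of this stands.
- **The orthostatic thresholds agree with protocol 12.3**, and SAP 8.4.3.5 also holds the seated criteria, so a programmer could follow those. True, but SAP 9.3.4 cites the whole of a section that contains both references and itself names only supine and standing.
- **The platelet sentence is probably a reversed label.** The limits are in /mm³, the factor is right in the other direction, and only central laboratory data are analyzed (SAP 9.3.3). Agreed.

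A reader might infer that C-SSRS severity will be lost, that platelet results will be a million times too large, or that the orthostatic results are invalid. The documents support none of these: they show faulty wording in derivation rules, not what was programmed or collected.

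**Conclusion.** Three texts are wrong or inconsistent as written, and each can be confirmed by reading.

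1. **C-SSRS (main point).** The low-to-high list conflicts with the 0-4 scale in its own section and in protocol 12.7, and it ranks a yes/no summary item. The effect on the most-severe table runs from none to complete: 0 to 15 of the 15 non-empty patterns in level 5, depending on how the eCRF is completed and level 5 is programmed. Other C-SSRS output is not affected. The wording of rules 2 and 3 also leaves it unclear whether self-injury alone counts as suicidal behavior.
2. **Orthostatic reference.** SAP 8.4.3.5 contradicts itself, and its hypotension definition, with SAP 9.3.4, departs from protocol 12.3. The number of subjects reclassified is unknown.
3. **Platelets (minor).** The direction of conversion is reversed in the text. Summaries would be wrong only if the rule were applied to data already in /mm³, and nothing in the documents shows that it would be.

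Confidence is high that the wording needs correcting. The consequences remain conditional on the eCRF and the programs.

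**What to change.** - **C-SSRS ranking (SAP 8.4.3.2).** Remove the summary item from the ranking and use it only as a flag for any behavior. Rank preparatory < aborted < interrupted < actual attempt, as in the 0-4 scale. Report completed suicide either as a separate item or as an explicitly added top level; if it is added, change the scale text to match, because the present scale ends at actual attempt.
- **C-SSRS counting (SAP 9.3.2).** Reword rules 2 and 3 so that non-suicidal self-injury is counted only under rule 4.
- **Orthostatic readings.** Reconcile SAP 8.4.3.5, SAP 9.3.4 and protocol 12.3 to one stated reference posture drawn from the paired readings that are collected. State how the 1- and 3-minute standing readings are used.
- **Platelets (SAP 8.4.3.3).** Correct the sentence, name the collected unit and the unit used for the PCSV limits and for the medication listing in SAP 9.1.5, and check the program.

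The cost is a few SAP wording changes and a check of the matching program lines, with no new data. The changes must be made before database lock. SAP 8.4.1.1 already reports an outcome of the data review meeting, so little time may be left.

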8.4.3.3. Laboratory Tests

Hematology tests will include: Red blood cell count, hemoglobin, hematocrit value, white blood cell count including differential, and platelet count.

Blood Chemistry will include: total bilirubin, direct bilirubin, CK, total cholesterol, triglycerides, BUN, bicarbonate, serum glucose, serum creatinine level, uric acid, sodium (Na), potassium (K), chloride, calcium (Ca), albumin and Gamma-glutamyl transferase (GGT).

Note: albumin will be included in the chemistry profile for Weeks 24, 48, 72 and 96 only. The Day 1/screening assessment will not include albumin as it was not collected as part of Study MT-1186-A01 chemistry profile. Thus, change from baseline cannot be calculated for albumin.

In addition, GGT will be obtained in only Japan country.

Qualitative urinalysis will include: protein, glucose, occult blood, urobilinogen, white blood cells, and bilirubin.

Unit conversion

In the platelet count unit, value is multiplied by 1000 to convert /mm³ to 10⁹/L.

Laboratory values below the limit of quantification

Laboratory values below 1/2 LLOQ (lower limit of quantification) will be used for BLQ (below the limit of quantification) for data summary statistics.

Handling of Reference Values and Indeterminate Values for Clinical Laboratory Test**Parameters**

If laboratory test value or its reference is indeterminate due to a problem with the test sample, then this value will be handled as a missing value.

Criteria for Potentially Clinically Significant Values (PCSV for laboratory):

The following criteria will be defined ^{8,9}

Chemistry

- ALT $\geq 3 \times$ Upper Limit of Normal Range (ULN), 5 \times ULN, 10 \times ULN, 20 \times ULN
- AST $\geq 3 \times$ ULN, 5 \times ULN, 10 \times ULN, 20 \times ULN
- ALT and/or AST $\geq 3 \times$ ULN, 5 \times ULN, 10 \times ULN, 20 \times ULN
- Total Bilirubin $\geq 2 \times$ ULN
- ALP > 400 U/L
- ALT or AST $> 3 \times$ ULN with Total Bilirubin $> 1.5 \times$ ULN
- ALT or AST $> 3 \times$ ULN with Total Bilirubin $> 2 \times$ ULN
- Hy's law (ALT or AST $> 3 \times$ ULN and ALP $< 2 \times$ ULN and Total Bilirubin $\geq 2 \times$ ULN)
- LDH $\geq 3 \times$ ULN
- BUN ≥ 30 mg/dL
- Serum Creatine ≥ 2.0 mg/dL
- Uric acid:
 - Male > 10.0 mg/dL,
 - Female > 8.0 mg/dL
- CK $\geq 3 \times$ ULN
- Chloride (Low) ≤ 90 mEq/L
- Chloride (High) ≥ 118 mEq/L
- Potassium (K) (Low) < 3.0 mmol/l
- Potassium (K) (High) > 5.5 mmol/l
- Sodium (Na) (Low) < 130 mmol/l
- Sodium (Na) (High) ≥ 150 mmol/l
- Calcium (Ca) (Low) < 7.0 mg/dL
- Calcium (Ca) (High) ≥ 12 mg/dL
- Concurrent Hepatic Abnormality:
 - ALT or AST $> 3 \times$ ULN with Total Bilirubin $> 1.5 \times$ ULN
 - Hy's law (ALT or AST $> 3 \times$ ULN and ALP $< 2 \times$ ULN and Total Bilirubin $\geq 2 \times$ ULN)

Hematology

- Hematocrit:
 - Male $\leq 37\%$ and decrease of ≥ 3 percentage points from baseline,
 - Female $\leq 32\%$ and decrease of ≥ 3 percentage points from baseline
- Hemoglobin:
 - Male ≤ 11.5 g/dL,
 - Female ≤ 9.5 g/dL
- White blood count (Low) $\leq 2800/\text{mm}^3$

- White blood count (High) $\geq 16,000/\text{mm}^3$
- Neutrophils Absolute count $< 1,000/\text{mm}^3$
- Platelet count (Low) $\leq 100,000/\text{mm}^3$
- Platelet count (High) $\geq 700,000/\text{mm}^3$

8.4.3.4. 12-Lead ECG

A 12-lead ECG will be performed after the subject has rested for at least 5 minutes in a supine position. The ECG will include the following numerical measurements: R wave to R wave (RR) interval, heart rate, QRS, QT, QTcB, and QTcF. The Investigator will perform an overall evaluation of the ECG for safety purposes and the recording will be reported as 'normal', 'abnormal CS', or 'abnormal NCS'.

The RR, QTcF and QTcB will be calculated using the below formulas, regardless of performed in CRF.

- RR (msec) will be calculated as $\{60 / \text{heart rate (beats/min)}\} * 1000$ and reported to integer.
- QTcF (msec) and QTcB (msec) will be calculated as $\{QT (\text{sec}) / RR (\text{sec}) ^ {(1/3)}\} * 1000$ and $\{QT (\text{sec}) / RR (\text{sec}) ^ {(1/2)}\} * 1000$ respectively and reported to integer.

8.4.3.5. Vital Signs

The following measurements will be collected: systolic and diastolic blood pressure, heart rate (e.g., beats per minute), respiratory rate, and axillary, oral or tympanic body temperature (eg, Celsius). The Investigator will perform an overall evaluation for safety purposes and the recording will be reported as 'normal', 'abnormal clinically significant (CS)', or 'abnormal not clinically significant (NCS)'.

Orthostatic Hypotension

Orthostatic hypotension will be defined as experiencing lightheadedness and/or dizziness and/or a reduction in systolic BP of 20 mmHg or more, and/or a reduction in diastolic BP of 10 mmHg or more, or increase in heart rate > 20 beats/minute for the standing measurement compared to the supine measurement.

The following criteria to determine "Orthostatic vital sign changes" are defined:

- Decrease of ≥ 20 mmHg from 'Seated (resting 5 minutes)' Systolic Blood pressure to 'Standing (after 1 minute)' Systolic Blood pressure
- Decrease of ≥ 20 mmHg from 'Seated (resting 5 minutes)' Systolic Blood pressure to 'Standing (after 3 minutes)' Systolic Blood pressure

Statistical Analysis Plan
Protocol No. MT-1186-A03

Mitsubishi Tanabe Pharma America, Inc.

- Decrease of ≥ 10 mmHg from 'Seated (resting 5 minutes)' Diastolic Blood pressure to 'Standing (after 1 minute)' Diastolic Blood pressure
- Decrease of ≥ 10 mmHg from 'Seated (resting 5 minutes)' Diastolic Blood pressure to 'Standing (after 3 minutes)' Diastolic Blood pressure
- Increase of > 20 bpm from 'Seated (resting 5 minutes)' Heart rate to 'Standing (after 1 minute)' Heart rate
- Increase of > 20 bpm from 'Seated (resting 5 minutes)' Heart rate to 'Standing (after 3 minutes)' Heart rate

The Investigator will also evaluate any clinical symptoms due to the orthostatic vital sign changes such as dizziness and lightheadedness.

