### 12.3 Orthostatic Vital Sign Measurement

The following vital signs measurements will be performed: systolic and diastolic blood pressure, and heart rate. Subjects must be in a seated position in a rested and calm state for at least 5 minutes before blood pressure assessments are conducted. Measure blood pressure and pulse rate. Have the patient stand. Repeat blood pressure and pulse rate measurements after standing 1 and 3 minutes. A drop in systolic blood pressure of  $\geq 20$  mm Hg, or in diastolic blood pressure of  $\geq 10$  mm Hg, or increase in heart rate  $>20$  beats/minute or experiencing clinical orthostatic symptoms (eg lightheadedness or dizziness) is considered abnormal. If subjects cannot stand due to disease progression or other reasons, it will not be considered a protocol deviation.

The Investigator will perform an overall evaluation for safety purposes and the recording will be reported as ‘normal’, ‘abnormal clinically significant (CS)’, or ‘abnormal not clinically significant (NCS)’.

Abnormalities of clinical significance will be reported as AEs.

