4.2. Sample Size and Power Considerations

The study sample size is not based on power and statistical considerations. This study serves as an extension to MT-1186-A01 (the Parent study) and, as such, will roll over subject to the current study. The total number of subjects enrolled will depend on the number of subjects who complete the MT-1186-A01 study and are also eligible and consent to participate in this extension study. Approximately 140 patients will potentially be enrolled in Study MT-1186-A03.

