7.2. Statistical Tests

This study is a long-term, open-label safety study. As a result, no formal hypothesis testing is planned for this study. The long-term safety and tolerability of oral edaravone will be evaluated in exploratory manner using descriptive statistics. For exploratory efficacy analysis, point estimates and their associated 95% Confidence Interval will be presented.

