9.3.4. Vital Signs

Vital sign measurements and their change from baseline will be listed and summarized using descriptive statistics by visit up to week 96. Those parameters will include: heart rate (HR), supine and standing blood pressure (BP) (both systolic and diastolic), body temperature and weight. Furthermore, supine minus standing blood pressure (both systolic and diastolic) and their change from baseline will be summarized with descriptive statistics by visit. The body weight values and change from baseline to each post baseline visit up to week 96 will be plotted by visit.

The number and percentage of subjects with orthostatic hypotension as defined in section 8.4.3.5 will be tabulated by visit.

9.3.5. 12-Lead ECGs

All ECGs parameters will be listed and analyzed.

The ECGs will be assessed by the investigator and deemed “Normal”, “Abnormal, not clinically significant” (Abnormal, NCS) and “Abnormal, clinically significant” (Abnormal, CS) and tabulated by visit up to week 96 using frequency counts and percentages.

In addition, the numerical ECG parameters and their change from baseline generated by the central ECG laboratory (see section 8.4.3.4) will be summarized by descriptive statistics for each parameter by visit.

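### SAP 8.4.3.5 lets a symptom or a heart-rate rise alone count as orthostatic hypotension, and the table in 9.3.4 will not show how many counted subjects had a pressure fall

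*SAP*

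**What the plan says.** SAP 8.4.3.5 (Vital Signs) opens its orthostatic paragraph with "Orthostatic hypotension will be defined as experiencing lightheadedness and/or dizziness and/or a reduction in systolic BP of 20 mmHg or more" and completes the list with "and/or a reduction in diastolic BP of 10 mmHg or more, or increase in heart rate > 20 beats/minute for the standing measurement", taking the supine reading as the reference. Below that it lists six separate criteria under the name 'orthostatic vital sign changes': systolic fall, diastolic fall and heart-rate rise, each at 1 and at 3 minutes of standing, and each measured from the seated reading. It adds that the investigator will evaluate symptoms arising from those changes.

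SAP 9.3.4 puts the definition to use: "The number and percentage of subjects with orthostatic hypotension as defined in section 8.4.3.5 will be tabulated by visit". It specifies no table of the six criteria and no breakdown of the count by component.

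Protocol 12.3 has essentially the same list, also joined by 'or', but reaches a different label: "experiencing clinical orthostatic symptoms (eg lightheadedness or dizziness) is considered abnormal". It does not use the term hypotension. SAP section 2 says that its statistical details supersede those in the protocol. SAP section 11, on changes from the protocol, does not mention the new label.

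**The concern.** A row labelled orthostatic hypotension will be read as the share of subjects whose blood pressure fell on standing. Under the SAP definition it is the share with any of five findings, three of which (lightheadedness, dizziness, faster heart rate) are not pressure measurements. A subject whose standing pressure is unchanged but whose heart rate is up by 21 beats/minute is counted. So is a subject who only feels lightheaded.

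What is at stake is the meaning of one named safety rate in a single-arm study. No control group shows how often non-specific symptoms or heart-rate responses occur. Because the count is not split, a reader of the tables cannot recover the number with a pressure fall.

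**Working it through.** The documents state no rate on this point, so there is no planned figure to reproduce. The check is of the logic, followed by an illustration on assumed rates.

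**1. Logic of the definition.** There are five yes/no components: lightheadedness, dizziness, systolic fall ≥20 mmHg, diastolic fall ≥10 mmHg, and heart-rate rise >20 beats/minute. Every connector is 'and/or' or 'or', so one component is enough.

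- Possible combinations: 2^5 = 32.
- Counted under the SAP definition: 32 − 1 = 31 (all except 'none present').
- Combinations with neither a systolic nor a diastolic qualifying fall: 2^3 = 8. Of these, 7 are still counted.
- Counted if only the two pressure criteria applied: 32 − 8 = 24.

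These are counts of logical patterns, not of subjects.

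**2. Direction.** With the reference posture held fixed:

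P(counted) = P(fall) + P(no fall, but a symptom or heart-rate rise).

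The second term cannot be negative, so the tabulated rate equals or exceeds the rate of qualifying falls.

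**3. Illustrative size.** Assumed inputs are fall 10%, any symptom 5% and heart-rate rise 3%. N = 140 is the approximate enrolment in SAP 4.2.

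- Independent components: 1 − (0.90 × 0.95 × 0.97) = 1 − 0.829 = 17.1%, about 24 subjects, against 14 with a fall. The share counted without a qualifying fall is (17.1 − 10)/17.1, about 41%.
- Complete overlap (symptoms and heart-rate rises occur only in subjects with a fall): 10%, no excess.
- No overlap: 10% + 5% + 3% = 18%.

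Varying the assumptions over fall 5–20%, symptoms 2–10% and heart-rate rise 1–5%, still independent:

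| Fall | Symptoms | Heart rate | Counted | Ratio to fall rate | Share without a fall |
|---|---|---|---|---|---|
| 20% | 2% | 1% | 22.4% | 22.4/20 = 1.1 | 11% |
| 10% | 5% | 3% | 17.1% | 17.1/10 = 1.7 | 41% |
| 5% | 10% | 5% | 18.8% | 18.8/5 = 3.8 | 73% |

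**4. Reference posture.**

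| Place | Standing is compared with |
|---|---|
| SAP 8.4.3.5, definition | Supine |
| SAP 9.3.4, difference summaries | Supine |
| SAP 8.4.3.5, six listed criteria | Seated |
| Protocol 12.3, measurement procedure | Seated |

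The supine reading belongs to the routine vital signs in protocol 12.2; the orthostatic procedure in 12.3 starts from sitting. Which posture is used decides who has a qualifying fall, so even a pressure-only count is not fully defined at present.

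**The case against.** The strongest reply is that this is a naming problem. The SAP counts essentially what protocol 12.3 calls abnormal, and nothing in the documents says that a pressure-only rule is the right one. That is fair as far as it goes: the composite is a legitimate screen. But the name in the table is hypotension, and the SAP itself separates pressure from heart rate a few lines later.

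A second reply is that other outputs cover blood pressure. SAP 9.3.4 summarises supine and standing pressures and their difference by visit. All data are listed. Protocol 12.3 has clinically significant orthostatic abnormalities reported as adverse events. These outputs limit the harm, and it would be wrong to say that the plan gives no other view of orthostatic pressure. None of them, however, gives the number of subjects with a qualifying fall; the listings would allow it only by reconstruction.

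Third, the study is descriptive: "As a result, no formal hypothesis testing is planned for this study". No error rate or power is affected. That stands.

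A reader might also infer two stronger points that the documents do not support:

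- **That a primary endpoint is misdefined.** The vital-signs endpoint in protocol 7.2.1 and SAP 3.2.1 names heart rate, respiratory rate, blood pressure and temperature, not the orthostatic assessment. Protocol 17.3.5.4 plans no orthostatic table.
- **That the rate will climb as the disease progresses and look like a drug effect.** The direction is unknown. Protocol 12.3 accepts that some subjects will be unable to stand, and SAP 7.1 takes visit percentages over non-missing observations, so progressing subjects may leave the table. The same SAP 7.1 rule already largely settles the denominator.

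**Conclusion.** The point holds as one of labelling and breakdown. As written, SAP 8.4.3.5 and 9.3.4 produce a rate called orthostatic hypotension that can include subjects with no qualifying pressure fall. For a fixed reference posture the rate cannot be lower than the rate of qualifying falls. This conclusion follows from the wording alone and needs no assumption.

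The size of the excess is not known. A reader might infer a severalfold inflation, but the ratios of 1.1 to 3.8 shown above come entirely from assumed rates and independence. If symptoms and heart-rate rises occur only in subjects who also have a fall, the excess is zero. The supine/seated conflict is a separate defect in the same section and needs resolving whichever label is kept.

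**What to change.** 1. In SAP 8.4.3.5, keep the term orthostatic hypotension for the SAP's own pressure criteria: a systolic fall of ≥20 mmHg or a diastolic fall of ≥10 mmHg on standing.
2. In SAP 9.3.4, tabulate by visit in separate rows: (a) orthostatic hypotension so defined; (b) heart-rate rise >20 beats/minute; (c) orthostatic symptoms, where recorded, since the SAP names no variable for them; (d) any of these, labelled 'abnormal orthostatic response' to match protocol 12.3.
3. Reconcile the reference posture across the definition, the six listed criteria, SAP 9.3.4 and protocol 12.3. State one reference and use it throughout, including in the difference summaries.

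The cost is SAP wording and a few extra table rows before database lock. No new data are needed.
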